A short baseline survey will be conducted at the time of initial outreach contact with FSW during the study period. The purpose of the baseline survey is to collect background information on FSW that may be used to assess whether FSW with different characteristics are more or less amenable to community HIV screening and HIV testing at health facilities. An application will be developed so that the survey can be completed and submitted to a server using mobile phones PL/PE/FSW. The following basic information will be gathered (see draft questionnaires for the baseline and post-test surveys in the annex of this protocol).

- Name (full name/initial)
- Age
- Date of birth

- Test Kit ID Number
- Education
- Marital status
- Age at initiation of sex work
- Number of clients last seven (7) days
- Methods of clients' recruitment (fixed facility, street, internet, online platform)
- Consistency of condom use
- Ever been tested for HIV
- When last time tested
- Ever been diagnosed with an STI (other than HIV)

In addition to these questions, FSW will be asked twelve (12) questions in the short version of anticipated HIV stigma scale (Reinius et al., 2017) designed to measure the extent to which participants anticipated negative intrapersonal and interpersonal consequences were they to contract HIV in the future. During data analysis, we will assess the ability of an index constructed from the data items collected to predict which FSW presented at health facilities for formal HIV testing. This will provide an estimate of the impact of anticipated stigma on HIV testing among FSW in Indonesia.

2. Post-test Survey

A short post-test survey will be conducted after the test has been taken. The purpose of post-test survey is to collect information of the experience of clients using the test kit and to record the test result. Some inquiries will be presented on a scale of 1-5, some inquiries will have binary answers (Yes/No, Reactive/Non-Reactive). The following inquiries will be made:

- The clarity of information being provided (flier or short video), on a scale of 1-5
- The easiness of test procedure, on a scale of 1-5
- Perceived accuracy of the test result, on a scale of 1-5
- The quality of response by the assigned contact person/hotline, on a scale of 1-5
- Clients' acceptance/perception towards the study procedure
- The likelihood of clients to recommend their peers to take the test, on a scale of 1-5
- Test result
- How likely is it that the client will get a HIV test at a health facility as a result of the community screening test, on a scale of 1-5
- Comments and suggestions.

3. Routine Recording

Because of limitations in the data recorded and reported by health facilities, the study will rely primarily upon data recorded by IU outreach staff. Modifications will be made to the data recording and reporting systems currently being used to facilitate collection of the data needed for the study in a manner that minimizes additional recording and reporting burden. The nature of the adjustments to be made will be different for "assisted" and "unassisted" community screening.

To capture the data needed for of this study, the following data need to be recorded:

No	Data Recorded	Intervention Group	Control Group
1	Number of FSW contacted via outreach that were at least 6 months since their last HIV test for whom testing at a health facility was recommended	Yes	Yes
2	Numbers of FSW offered for HIV test at health facility	Yes	Yes
3	Numbers agreeing and disagreeing to testing at a health facility	Yes	Yes
4	Of those agreeing to getting tested at a health facility, the numbers that actually went to a health facility and were tested for HIV	Yes	Yes
5	Number of FSW offered for OFT screening	Yes	No
6	Among FSW not agreeing to be tested at a health facility, the numbers that agreed to (1) assisted community HIV screening and (2) unassisted community HIV screening	Yes	No
7	Numbers that were actually screened, assisted and unassisted	Yes	No
8	The number of community screening tests that were reactive	Yes	No
9	Among FSW with reactive community screening tests, the numbers that were subsequently tested at a health facility	Yes	No
10	Number of FSW initiating ART	Yes	Yes

For **unassisted** approach, additional information will be gathered as indicated below:

1. Numbers of FSW who access the link online
2. Numbers of FSW who are deemed eligible
3. Numbers of FSW who fill in baseline survey and agree to participate
4. Numbers of FSW who agree to take HIV test at health facility
5. Numbers of FSW who request the kit being delivered vs picking-up at fixed location
6. Numbers of FSW who upload the test result
7. Numbers of reactive vs non-reactive test result
8. Numbers of FSW who complete the post-test survey

9. Among FSW with community screening tests, the numbers that were subsequently tested at a health facility (reactive OR non-reactive)
10. Number of FSW initiating ART

4. Numbering System for Test Kit and Other Instruments

a) Recording Test Kit ID

Every test kit will have a unique ID number, which will later be referred to as the Kit ID number. The Kit ID Number is to be filled in on all instruments and forms that are to be linked to the test results (e.g., baseline survey, test results form, post-test survey, routine data record in each IU, etc.). This number needs to be identified at all times to make sure that each participant is only assigned to one test kit, matching the kit with the results, and to track the stock of the test kit remained. The format of this ID kit will be “01-001”, where the first 2 digits are to identify the number of the district in which participants take the test, and the last 3 digits are to identify which test kit the participant is using. This test kit ID will also be later used for each IU to track the distribution of the test kit. Every test kit being distributed, either in a fixed place or delivered through same-day delivery services, will be recorded and tracked by each IU. An MS Excel or MS Access form will be developed to record and track the Kit ID Number.

b) Recording temporary FSW ID

On the ground of confidentiality, participants' full name will not be revealed and used within this study. A new system to ensure the reliable yet confidential identification of study participants needs to be established. Every participant in the study will be assigned to a temporary FSW ID. The format will be **the first 4 letters of participants' names added by the date of birth (yy/mm/dd)**. For example, a participant named “INDRIYANTI” who was born on March 5th 1976, her temporary FSW ID will be “INDR760305”. For FSW whose name contains only 3 letters, the number zero will be added after the last letter. For example, an FSW whose name is “AYU” and was born on March 5th 1976, her temporary will be “AYU0760305”. This temporary FSW ID will be used to ensure that each participant is only assigned to one test kit, to track test results, and to be filled in the baseline and post-test survey.

c) Matching Test Kit ID and temporary FSW ID

To match the test kit ID and temporary FSW ID, an automatic system needs to be developed to detect it precisely. This way, we can be sure that each participant only gets to participate in this study once (from receiving the kit, performing the test, and reporting the result).

d) Paper Based Data Collection

In the event that participants' data are collected by paper, a procedure to upload the data into the established online system will be developed. Each data manager in the IUs needs to conduct the procedure regularly. This is to ensure that all data are being captured thoroughly.

F. DATA ANALYSES

The data analyses to be undertaken will be directed to addressing the research questions laid out at the beginning of the protocol and statistical tests appropriate to each specific analysis will be performed to inform the interpretation of results. The specific steps in the data analysis will be as follows:

1. Compare the characteristics of FSWs who receive self-testing and blood testing.

2. Compare the characteristics of FSWs who receive assisted and unassisted self-testing.
3. Compare proportion of FSWs taking confirmatory test out of those who receive the test in the assisted and unassisted self-testing.
4. Compare the proportion of FSWs who receive HIV test out of those who got offered for the test (including self-testing) in the intervention group with proportion of FSWs who receive HIV test in the control group.
5. Compare the proportion of FSWs taking confirmatory test (including self-testing) out of those receive the test in intervention groups and control group.
6. Compare the proportion of HIV positive in the assisted, unassisted (intervention) and HIV positive in the control group.
7. Compare the proportion of ART initiation in the assisted, unassisted (intervention) and the control group.
8. Calculate the cascade of HIV testing and treatment.
9. Compare stigma scores and FSWs who went to a health facility for HIV testing between assisted, unassisted group.
10. Compare the HIV and STI risk behaviors between assisted and unassisted group.

G. CONTINGENCY STUDY DESIGN

Should the OraQuick® test kits not become available in sufficient time to conduct a full-scale cRCT, a smaller-scale study will instead be undertaken. The purpose of the smaller study is the same as the cRCT described above, and the same protocol described above will be implemented. But the comparison is achieved targets between before and after intervention – there will be no comparison districts. The study will be undertaken in three (3) districts. The three districts will be selected from different parts of Indonesia, and they are: Kota Bandung (west part of Indonesia), Kota Denpasar (central part of Indonesia), and Kota Makassar (center-east part of Indonesia).

The primary limitations of the smaller-scale study are (1) the districts were not randomly chosen and (2) the proportion of HIV testing before and after intervention that might not sufficient to produce a statistically significant result to prove the success of the intervention. This smaller-scale version of the study should be viewed as a demonstration or pilot project leading to a bigger study afterwards.

Data analysis will be done by comparing changes in outcome variables measured against results in the four semesters prior to the study in the 3 districts compared to the other 20 acceleration districts.

Analysis of outcome variables are similar with the cRCT approach as below:

1. Compare the characteristics of FSWs who receive self-testing and blood testing in 3 districts.
2. Compare the characteristics of FSWs who receive assisted and unassisted self-testing 3 districts.
3. Compare proportion of FSWs taking confirmatory test in the assisted and unassisted self-testing 3 districts.

4. Compare the proportion of FSWs who receive HIV test including self-testing in the intervention group with proportion of FSW who receive HIV test in the control group (in 3 districts before the intervention and other 20 acceleration districts).
5. Compare the proportion of FSWs taking confirmatory test (including self-testing) in the intervention group with proportion of FSW who receive HIV test in the control group (in 3 districts before the intervention and the other 20 acceleration districts).
6. Compare the proportion of HIV positive in 3 districts (assisted and unassisted) and HIV positive in the control group (in 3 districts before the intervention and other 20 acceleration districts).
7. Compare the proportion of ART initiation in 3 districts (assisted and unassisted) and the control group (in 3 districts before the intervention and other 20 acceleration districts).
8. Calculate the cascade of HIV testing and treatment.
9. Compare stigma scores and FSW who went to a health facility for HIV testing.
10. Compare the HIV and STI risk behaviors.

H. RESEARCH ETHICS AND PERMISSION

[figure not shown]
Participation in the study will be entirely voluntary. For the assisted testing, formal signed consent or witnessed verbal informed consent will be obtained by outreach workers. Records of informed consent will be managed /safeguarded using sealed envelope with unique number. To ensure the confidentiality, in the base line data only unique number will be recorded. A draft of the informed consent form can be found in Annex-3 of this protocol.

For unassisted screening, every study participant should fill in the check box of website or application to provide consent: “By signing this form/ticking this box, I understand that I am thereby agreeing to enroll in this study” and test kit is not sent out if the check box is not checked by the user.

This protocol will be reviewed by the Faculty of Medicine Udayana University Institutional Review Board (IRB) prior to study initiation. Approval of the protocol in either its original or modified form is required.

Research permission will be submitted to Department of Internal Affairs Republic of Indonesia, which will subsequently be referred to the licensing office in each provinces and priority districts.

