The flowchart of the study is presented in Figure 1. Randomization was carried out among the 23 priority districts in this study with a ratio of 2:1 (that is, 2 intervention districts per 1 control district). The details of randomization are explained in section B.4 of this document. **The assigned 15 intervention districts and 8 comparison districts** are described in Table 6. Potential participants in the intervention area will be screened through the inclusion and exclusion criteria established for

this study. The criteria for participants who are eligible for this study are explained in section B.3 of this document and Annex2.

According to the Indonesian Ministry of Health's current recommendation, HIV blood test at an authorized health facility is still the current practice for HIV diagnosis. Both participants in the intervention and comparison area will be offered for HIV blood test at a health facility. Participants in comparison areas and participants in intervention areas who agree to take HIV test at a health facility will then be managed further according to the existing guideline or "standard of care." For participants in intervention areas who refuses to have her blood drawn for HIV test at a health facility will then be offered self-testing using OraQuick®. Participants will then fill and sign the informed consent to participate in CBS study.

Next, participants will be offered to do the test assisted or unassisted. If the participant chooses to perform the test assisted, the PL/PE will help her from filling in a baseline survey, performing the test, and filling in a post-test survey. If the participant chooses to perform the test unassisted, there will be two options for the participant to get the test kit. First, PL/PE will deliver the test kit for the participant, help with filling in the baseline survey on the spot and give information about uploading test results and the post-test survey, along with a hotline number to call for any questions and concerns, including follow-up steps after participants have received the results. The second method, participants will be given a link online which will entitle information of this study, eligibility criteria, informed consent, baseline survey, link to order a test kit, link to upload result and link to fill in the post-test survey. Participant who chooses this second method will also be given hotline number should there be any further inquiries.

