3.1 Study kick-off										
3.2 Data collection										
4. Data analysis and report writing										
5. Workshop for study finding dissemination										

3. Eligibility Criteria

The target audience for the intervention to be evaluated are FSW in Intervention districts that meet the criteria outlined below.

Inclusion criteria

- Women, 18 years or older at enrolment
- Reports transactional sex (vaginal, oral and/or anal) at least once in the past month
- No HIV test in last 6 months
- Self-reported HIV negative OR HIV status unknown

Exclusion criteria

- Unwilling to participate for any reason
- Concurrently participating in another HIV prevention study

4. Randomization

Stratified randomization was carried out for the 23 priority districts involved in this study. First, sampling strata were created by sorting the mean average value of achieved HIV testing target per semester from 2018-2019 in each district from the largest to the smallest. The second step was to sort the districts into eight groups of three districts, except for the last group which will only consist of two districts. Randomization for intervention and comparison group were then carried out within these groups of eight with 2:1 ratio (2 intervention: 1 comparison).² The results of stratified randomization are presented in Table 6. In separate table, Table 7 contains 15 intervention districts and Table 8 contains 8 comparison districts.

² A 2-to-1 intervention to comparison district ratio was chosen in order to increase the likelihood of recruiting a sufficient number of FSW for community screening to reach the sample size target considering the relatively short time frame available for for study implementation.

Table 6. Allocated intervention group and comparison group

No	Kab/Kota	Region	Achieved target of HIV testing per semester (2018-2019)	Group
1	Kota Denpasar	3	982	Intervention
2	Kota Makassar	3	866	Comparison
3	Kota Palembang	1	694	Intervention
4	Kota Jakarta Utara	1	612	Comparison
5	Kota Medan	1	575	Intervention
6	Kota Surabaya	3	568	Intervention
7	Kota Jakarta Barat	1	544	Intervention
8	Kota Bandung	2	487	Comparison
9	Kota Jakarta Timur	1	479	Intervention
10	Kota Jakarta Pusat	1	473	Intervention
11	Kota Jakarta Selatan	1	448	Comparison
12	Kota Sorong	4	415	Intervention
13	Kab. Tangerang	1	391	Intervention
14	Kota Bogor	2	374	Intervention
15	Kota Jayapura	4	323	Comparison
16	Kota Bandar Lampung	1	319	Comparison
17	Kota Depok	2	287	Intervention

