18	Kota Malang	3	243	Intervention
19	Kota Tangerang Selatan	1	184	Intervention
20	Kota Bekasi	2	158	Comparison
21	Kota Surakarta	2	144	Intervention
22	Kota Semarang	2	129	Comparison
23	Kab. Deli Serdang	1	80	Intervention

Table 7. Allocated intervention districts

No	Kab/Kota	Region	Achieved target of HIV testing per semester (2018-2019)	Group
1	Kab. Deli Serdang	1	80	Intervention
2	Kota Medan	1	575	Intervention
3	Kota Palembang	1	694	Intervention
4	Kab. Tangerang	1	391	Intervention
5	Kota Tangerang Selatan	1	184	Intervention
6	Kota Jakarta Barat	1	544	Intervention
7	Kota Jakarta Pusat	1	473	Intervention
8	Kota Jakarta Timur	1	479	Intervention
9	Kota Bogor	2	374	Intervention
10	Kota Depok	2	287	Intervention
11	Kota Surakarta	2	144	Intervention
12	Kota Surabaya	3	568	Intervention
13	Kota Malang	3	243	Intervention
14	Kota Denpasar	3	982	Intervention
15	Kota Sorong	4	415	Intervention

Table 8. Allocated comparison districts

No	Kab/Kota	Region	Achieved target of HIV testing per semester (2018-2019)	Group
1	Kota Bandar Lampung	1	319	Comparison
2	Kota Jakarta Utara	1	612	Comparison
3	Kota Jakarta Selatan	1	448	Comparison
4	Kota Bekasi	2	158	Comparison
5	Kota Semarang	2	129	Comparison
6	Kota Bandung	2	487	Comparison
7	Kota Makassar	3	866	Comparison
8	Kota Jayapura	4	323	Comparison

5. Recruitment and Sample Size

All FSW in intervention districts who meet study eligibility criteria will be offered community screening (see Section C below for intervention implementation guidelines). FSW in comparison districts will continue to receive the current standard package of interventions.

In to be able to detect a 10 percentage point difference in the rate of HIV testing at health facilities between FSW in intervention vs. comparison districts and have 95% certainty that a difference of that magnitude would not have occurred by chance and 90% certainty of detecting a difference of this magnitude if the difference was real/”the truth,” the following sample of FSW will be needed in intervention and in comparison districts:³

$$n \geq [Z_{1-\alpha} (2P(1-P))^{1/2} + Z_{1-\beta} (P_1(1-P_1) + P_2(1-P_2)^2 / (P_1-P_2)^2)] * deft$$

Where:

$Z_{1-\alpha}$ = the Z score for the level of statistical confidence, or statistical precision, desired (for 95%, $Z = 1.96$)

$Z_{1-\beta}$ = the Z score for the desired statistical power (for 90% one-sided test, $Z = 1.282$)

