P_1 = the expected population proportion in the comparison group of districts (set = 0.5 – this is the worst-case scenario and will produced a sample size that is adequate irrespective of the actual proportion)

P_2 = the expected population proportion in the intervention group of districts (set = 0.6 – assume minimum effect size to be realized of 10 percentages points)

$$P = (P_1 - P_2) / 2$$

$(P_1 - P_2)$ = the magnitude of comparison-group differences (or change over time) to be detected with the specified level of precision and power (assumed to be +/- 10 percentage points)

deft = design effect to compensate for clustering at the district level (1.5 assumed).

The required sample size is thus $n \geq 635$ per experimental group; ≥ 761 after 20% allowance for lost-to-follow up

³ Source: Lwanga SK and Lemeshow S. Sample Size Determination in Health Studies: A Practical Manual. Geneva: World Health Organization.

Interpretation: we would need to recruit 761 FSW who self-test for HIV testing in the intervention districts and 761 FSW for HIV testing at health facilities in comparison districts to be able to detect a 10 percentage point difference in the rate of HIV testing at health facilities (intervention vs. comparison districts) to have 95% certainty that a difference of that magnitude would not have occurred by chance and 90% certainty of detecting a difference of this magnitude if such a difference existed.

In order to assess whether “assisted” or “unassisted” community HIV screening among FSW results in a larger increase in the rate of HIV testing at health facilities, we would need samples of size $n \geq 761$ each of FSW who received assisted and unassisted screening in intervention districts, a total of $n \geq 1,522$ FSW in intervention districts, plus $n \geq 761$ in comparison districts.

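### The stated 635 (761) women per group does not follow from the inputs in Section B.5, the design effect of 1.5 is unsupported for 15 versus 8 districts, and Section F names no analysis that respects district randomisation

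*Combined protocol and SAP*

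**What the plan says.** Section B.5 defines the significance term as "the Z score for the level of statistical confidence, or statistical precision, desired (for 95%, $Z = 1.96" and the power term as "the Z score for the desired statistical power (for 90% one-sided test, $Z = 1.282". The expected proportions are 0.5 in comparison districts and 0.6 in intervention districts. The difference is described as one "to be detected with the specified level of precision and power (assumed to be +/- 10 percentage points". The clustering factor is "deft = design effect to compensate for clustering at the district level (1.5 assumed". The result is 635 "per experimental group; ≥ 761 after 20% allowance for lost-to-follow up". The 761 is then used three times: assisted, unassisted (together 1,522 in intervention districts) and comparison.

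The randomised unit is the district. Section B.4 reports that "Stratified randomization was carried out for the 23 priority districts involved in this study", and Section B.1 gives "The assigned 15 intervention districts and 8 comparison districts". Neither number appears in the sample size calculation.

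Section F lists ten analysis steps. The main between-group step begins "Compare the proportion of FSWs who receive HIV test out of those who got offered for the test". The introduction to that section promises tests suited to each analysis. It mentions no cluster-level test, mixed model, estimating equations, adjustment for strata or small-sample correction.

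**The concern.** The plan presents itself as a community randomised trial that will give strong evidence on facility testing. Three things behind that claim do not fit together. The sample size cannot be recovered from the values printed beside it. The clustering allowance is one unexplained number, although its effect depends on the ICC and on how many districts carry each group. And the analysis section leaves open whether the comparison will treat the district or the woman as the unit.

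At stake are the 90% power statement, which is wrong as written, and the validity of the main p-value, which depends on a choice the plan has not made.

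**Working it through.** **Inputs (Section B.5).** P1 = 0.5, P2 = 0.6, power Z = 1.282, multiplier 1.5, loss allowance ×1.2. P is printed as half the difference, which is negative and has no real square root in the formula; I take the mean, 0.55. I also read the misplaced square and bracket in the printed formula as the standard form:

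n = [Z·√(2·0.55·0.45) + 1.282·√(0.25 + 0.24)]² / 0.10²

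**1. Reproducing the plan's figure.** Two routes give it.
- Z = 1.645, multiplier 1.5: (1.1574 + 0.8974)² / 0.01 = 422.2, rounded up to 423. Then 423 × 1.5 = 634.5, and × 1.2 = 761.4.
- Z = 1.96, multiplier √1.5 ≈ 1.22: (1.3790 + 0.8974)² / 0.01 = 518.2. Then 518.2 × 1.2247 = 634.7, and × 1.2 = 761.6.

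Continuity correction, unpooled variance, 2:1 allocation and 80% power do not give 635 at Z = 1.96 and 1.5.

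**2. Using the inputs as written.** Z = 1.96, multiplier 1.5: 518.2, rounded up to 519. Then 519 × 1.5 = 778.5, i.e. 779, and 778.5 × 1.2 = 934.2, i.e. about 935.

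**3. Power of the stated numbers at design effect 1.5, two-sided 5%.**
- 635 per group: effective n = 635/1.5 = 423.3. Power = Φ[(0.10·√423.3 − 1.3790)/0.7] = Φ(0.97) = 83.4%; with the unpooled standard error, 83.6%.
- 761 per group, no loss: effective n = 507.3. Power = 89.4% to 89.6%.

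**4. What 1.5 implies.** With equal district sizes, design effect = 1 + (m − 1)·ICC, so ICC = 0.5/(m − 1).

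| Women per group | m over 15 districts | ICC | m over 8 districts | ICC |
|---|---|---|---|---|
| 635 | 42.3 | 0.012 | 79.4 | 0.006 |
| 761 | 50.7 | 0.010 | 95.1 | 0.005 |

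With equal numbers of women per group, one ICC cannot give 1.5 in both groups.

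**5. Power for 15 versus 8 districts.** The documents give no ICC, so these values are assumptions. SE² = 0.24·D_I/n_I + 0.25·D_C/n_C, where D_I and D_C are the design effects in the intervention and comparison groups, each 1 + (m − 1)·ICC. Power is two-sided 5%, noncentral t, 21 df, equal district sizes.

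| ICC (assumed) | 635 vs 635 | 761 vs 761 | 1,522 vs 761 |
|---|---|---|---|
| 0.005 | 85% | 90% | 94% |
| 0.01 | 77% | 82% | 87% |
| 0.02 | 64% | 67% | 72% |

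Example, 761 vs 761 at 0.01: D_I = 1.497, D_C = 1.941, SE = 0.0333, 0.10/SE = 3.00, power 82%.

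Unequal sizes lower this. Replacing m by m(1 + CV²) with an assumed size CV of 0.6 gives design effects 1.680 and 2.284, SE = 0.0358 and power of about 76%. For scale, the Table 4 counts run from 80 to 982.

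**6. If districts were ignored.** At design effect 1.5 the false-positive rate of a nominal 5% test is 2·[1 − Φ(1.96/√1.5)] = 2·[1 − Φ(1.600)] = 11.0%.

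**The case against.** The tempting reading of step 1 is that a one-sided calculation was mislabelled. The subscript 1−α, the words about a one-sided test beside the power term and the directional objectives all point that way. The documents do not establish it. The √1.5 route keeps the written Z and needs no intermediate rounding, and *deft* is a common survey symbol for the square root of a design effect. Against that route, Section B.5 calls 1.5 the design effect itself. Both explanations stay open; what is certain is that 635 does not follow from 1.96 and 1.5 together. Nor does the plus-or-minus sign settle sidedness, because it is attached to the size of a difference or of a change over time.

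The practical effect of the arithmetic slip alone is modest. The totals are minimums, all eligible women in intervention districts are to be offered screening, and 1,522 versus 761 at a design effect of 1.5 would have about 96% power (two-sided z). That stands, and it is why no extra enrolment is asked for.

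A reader might also infer that Section F treats women as individually randomised. It does not say so: it promises suitable tests, and Section B.5 recognises clustering. The 11% is conditional on districts being ignored. But Section F does not exclude that choice, and the multivariable analyses mentioned in Section B.5 concern confounding in programme (SIHA) data, not clustering.

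Finally, ICCs well above 0.02 might be inferred from the Table 4 and Table 5 counts. Those counts reflect testing quotas (Section C.4) and all women reached, not women offered a test, so higher values are illustrative only. The power table also has limits: it assumes equal district sizes, and fitting all eight strata would leave 23 − 8 − 1 = 14 df rather than 21.

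**Conclusion.** The point holds and must be fixed. As written, the inputs require about 779 women per group (935 with the allowance), not 635 (761). At design effect 1.5 and two-sided 5%, the stated numbers give 83-84% and about 89% power. This rests on P = 0.55 and on reading the formula in its standard form. How the sponsor reached 635 is not known.

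The 1.5 has no ICC or source and does not use the district counts. Whether 23 districts support 90% power depends on an ICC that the plan never states: 761 versus 761 reaches 90% at an assumed 0.005 but 67% at 0.02, with equal district sizes. It does not follow that the trial is underpowered, since the true ICC could lie at either end.

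Section F leaves the unit of analysis unspecified. That is a gap, not a prescribed error.

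**What to change.** **1. Section B.5, arithmetic.** State whether the test is one- or two-sided, and whether 1.5 is the design effect or was applied as its square root. Then make Z, multiplier and n agree.
- Two-sided with design effect 1.5: restate about 779 (935), or keep 635 (761) and state 83-84% (89%) power.
- One-sided intended: say so and write Z = 1.645.
- √1.5 applied: say so, and state that the variance inflation allowed for is only about 1.22.

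Correct the printed expression for P at the same time. No extra enrolment is required.

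**2. Section B.5, clustering.** Replace the flat 90% claim with power for 15 versus 8 districts over a range of ICCs labelled as assumptions. For example, at 0.005 / 0.01 / 0.02: 761 versus 761 gives 90 / 82 / 67%, and 1,522 versus 761 gives 94 / 87 / 72%. State the method (two-sided t, 21 df), that equal district sizes are assumed, and that unequal sizes lower power (about 76% for 761 versus 761 at 0.01 with a size CV of 0.6). Label any higher ICC as illustrative.

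**3. Section F.** Add: *Intervention and comparison districts will be compared by an analysis that respects district randomisation: linear regression of the 23 district proportions on group, or a mixed model with a district random effect and a small-sample correction, adjusted for the Table 4 value used to form the strata.* Choose one of the two before outcome data are seen.

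**Cost.** Protocol and SAP wording and some analyst time; the adjustment value is already in Table 6. The downside is a lower stated power and one degree of freedom. Going from 21 to 20 df costs under half a percentage point of power in the scenarios above (for example 81.6% to 81.5% for 761 versus 761 at 0.01).

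### The sample size of 635 per group (761 with losses) does not follow from the stated inputs: at Z = 1.96 it gives about 82% power, not 90%

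*Combined protocol and SAP*

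**What the plan says.** Section B.5 (Recruitment and Sample Size) of the combined protocol and SAP gives a two-proportion formula with these inputs:

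- Confidence: "the Z score for the level of statistical confidence, or statistical precision, desired (for 95%, $Z = 1.96".
- Power: "for 90% one-sided test, $Z = 1.282".
- Comparison districts: "the expected population proportion in the comparison group of districts (set = 0.5".
- Intervention districts: "the expected population proportion in the intervention group of districts (set = 0.6".
- Difference: "assumed to be +/- 10 percentage points".
- Clustering: "deft = design effect to compensate for clustering at the district level (1.5 assumed".

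The average proportion P in the formula is printed as (P1 - P2)/2. The result is "635$ per experimental group; ≥ 761 after 20% allowance for lost-to-follow up". The interpretation that follows claims, for 761 versus 761, 95% confidence and "90% certainty of detecting a difference of this magnitude". The same 761 is then used for each of the assisted and unassisted groups (1,522 in intervention districts) and for the comparison districts.

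**The concern.** The result is smaller than the stated inputs can produce. A calculation with Z = 1.96, 90% power and a design effect of 1.5 for 50% versus 60% should come out well above 635. The loss allowance also looks short, because adding 20% to a number does not offset losing 20% of the enlarged number.

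Two things are at stake. The plan promises 90% power, and a null result would be read against that promise. The error also carries into all three group targets, including assisted versus unassisted, which is one of the primary questions in section A.6. In addition, the stated Z and the stated n imply different sidedness and section F names no test, so the choice between 1.645 and 1.96 is left open until the data are in.

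**Working it through.** **Inputs, all from section B.5:** P1 = 0.5, P2 = 0.6, Z for confidence = 1.96, Z for power = 1.282, design effect = 1.5, loss = 20%.

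**Formula.** The standard form of the printed expression is

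n = [Zα·√(2P(1-P)) + Zβ·√(P1(1-P1) + P2(1-P2))]² / (P1-P2)², then multiplied by the design effect.

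The printed P gives (0.5 - 0.6)/2 = -0.05, so P(1-P) is negative and has no real square root. I used the average, P = 0.55. Then √(2 × 0.55 × 0.45) = 0.7036 and √(0.25 + 0.24) = 0.7.

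**Reproducing the plan's figure.** Z = 1.645 reproduces it:

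- (1.645 × 0.7036 + 1.282 × 0.7)² / 0.01 = 422.2, rounded up to 423.
- 423 × 1.5 = 634.5, hence 635.
- 634.5 × 1.2 = 761.4, hence 761.

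**With the stated Z = 1.96:**

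- (1.96 × 0.7036 + 1.282 × 0.7)² / 0.01 = 518.2.
- 518.2 × 1.5 = 777.3, so about 778 (779 if 518.2 is rounded up to 519 first).
- The plan's 635 is about 18% below this: (778 - 635)/778.

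**Other routes to 635.** The other variants within 3% of 635 also need 1.645: unpooled variance gives 630, and P = 0.50 gives 637. With Z = 1.96, the nearest results are 612 (80% power with continuity correction) and 664 to 669 (85% power). Both contradict the stated 90%.

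**Loss allowance.**

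- 761 × 0.8 = 609 analysed, below 635.
- To retain 635 after 20% loss: 635/0.8 = 794.
- To retain 778 after 20% loss: 778/0.8 = about 973. The plan's 761 is about 22% below that.

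**Power at the plan's own size.** Power = Φ[(0.1·√(N/1.5) - Zα × 0.7036)/0.7], with N analysed per group:

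| N analysed per group | Z = 1.96 (two-sided 5%) | Z = 1.645 (one-sided 5%) |
|---|---|---|
| 635 | 83.4% | 90.1% |
| 609 (761 less 20%) | 81.8% | 89.0% |
| 761 (no loss) | 89.4% | 94.1% |

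The Z value accounts for most of the shortfall (90% to about 83%). The loss inflation takes off roughly another 1.6 points.

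**The case against.** The strongest reply is that the plan never says the test is two-sided. The symbol is written Z with subscript 1-α, not 1-α/2. The words one-sided test appear, although attached to the power term, and several objectives are phrased as increases. On that reading, power is 90.1% at 635 and 89.0% at 609, and the fault shrinks to one wrong Z value. This is fair as far as it goes: 82% is conditional on a two-sided 5% test. But that is the test that Z = 1.96 implies, and if a one-sided test was meant, the printed 1.96 is wrong. The text is inconsistent either way.

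It can also be said that the use of 1.645 is inferred. That is true. The match depends on rounding up before applying the design effect, and the plan prints no such value. The discrepancy between 635 and about 778 does not depend on the explanation.

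A third point is that pooling all 1,522 intervention participants against 761, less 20%, gives about 91% power two-sided at the same design effect. This is correct, but the plan claims 90% for 761 versus 761, and pooling does nothing for assisted versus unassisted.

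Finally, the error in P changes none of the plan's numbers, and the loss inflation is a small part of the shortfall. Both are secondary. The brackets and exponents in the printed formula may have been damaged in PDF conversion, and nothing here rests on them.

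**Conclusion.** The concern holds. The stated inputs require about 778 analysed per group, or about 973 recruited with 20% loss. The plan states 635 and 761. At its own recruitment target, with its own 20% loss, power for 761 versus 761 is about 82% at Z = 1.96, so the risk of missing a true 10-point difference is about 18%, not 10%. If a one-sided 5% test is declared instead, power is about 89%, close to the claim.

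All these figures rest on the plan's 50% versus 60% and on its assumed design effect of 1.5, for which it gives no supporting intracluster correlation. The 82% applies to each comparison of two groups of 761, including assisted versus unassisted.

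**What to change.** In section B.5, choose one sidedness and make Z, n and power agree. Without changing recruitment, either of these would do:

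- Two-sided 5%, Z = 1.96, 761 recruited and 609 analysed per group, about 82% power.
- One-sided 5%, Z = 1.645, 761 recruited and 609 analysed per group, about 89% power.

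State that the figure is conditional on a design effect of 1.5. Correct P to (P1 + P2)/2 and the loss inflation to n/(1 - 0.20). Carry the same statement through to the assisted and unassisted targets, and name the same sidedness for the tests in section F.

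The cost is wording only, and the stated power becomes less favourable. Keeping both Z = 1.96 and 90% power would instead need about 973 recruited per group, or 973 - 761 = 212 more in each.
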